4.5 Postoperative Examination

Only if the planned number of 388 eyes is not reached by sending a questionnaire to the patients, the patients, who could not provide information because of uncertainty, are brought to the Eye Hospital Neubrandenburg for the assessment of the postoperative PCO. In this case, a proband study insurance and a travel insurance will subsequently be paid.

As part of the study, the following investigations are then carried out:

- a) General and ophthalmological patient's history
 - Questionnaire on general and ophthalmological medication
 - General pre-existing conditions
 - Previous operations
- b) Best corrected visual acuity
 - ETDRS Panel / Snellen Panel: Letters on panels with decreasing size from top to bottom to determine the visual acuity
- c) Slit lamp examination
 - Eye examination with the help of a microscope to observe the eye under high magnification to assess the anterior, middle and posterior structures of the eye
- d) Assessment of posterior capsule (possibly with dilated pupil)

The newly obtained findings are then supplemented in the data collection table.

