2.2 Population

- Up to 3000 patient's eyes should be recruited
- Patients after cataract surgery with implantation of MICS-IOL L-313

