2.4 Study-investigation-plan

- intraoperative und postoperative data gathering from the medical records
- Filing a questionnaire to the patients, asking for diagnosis and treatment of PCO (if necessary, a postoperative examination in the Department of Ophthalmology Neubrandenburg in order to determine the PCO, if no PCO was documented or if not known)

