4.2 Patients recruitment

For statistical evaluation, the number of cases is determined using the following formula * before patient recruitment.

$$n = 16 \times \frac{\delta^2}{d^2}$$

n=Subjects number
δ=Standard deviation
d= relevant difference

$$n = 16 \times \frac{0,492^{2**}}{0,1^2} = 387,88 \approx 388 \text{ Patients}$$

80% of the patients eligible for the study underwent surgery 3 to 5 years ago. At a follow-up period of 3 to 4 years, the response rate is 13.9% ***.

This results in:

$$n = \frac{388}{0,139} = 2.791,37 \approx 2.792 \text{ Patients}$$

Due to the relatively high average age (at the time of the operation) of 74.73 years, an even lower response rate is to be expected. For this reason, up to 3000 patients will be contacted.

The patient receives the patient's study information sheet, the declaration of consent as well as an informative sheet for the patients regarding PCO. While retaining one copy of these documents, the patient is required to return the other copy and the completed data collection form to the eye clinic. Only when the signed declaration of consent is present, the patient participates in the study.

*Kutschmann M et al. Aspekte der Fallzahlkalkulation und Powerberechnung anhand von Beispielen aus der rehabilitationswissenschaftlichen Forschung. Rehabilitation 2006;45:377-384

** Zur Vergleichsbasis sind 2 Publikationen mit dem Thema der nachstarquote herangezogen worden:

1. Peterman K, Wildgrube M „A-Konstante und Nachstarquote der Intraokularlinse Akreos™ AO MI-60“, Oktober 2009,
2. Spyridaki M, Höh H „Vergleich von 4 MICS-Intraokularlinsen (ThinLens, AcriSmart, CareFlex, und Acriflex) im Hinblick auf ihre Neodym:YAG-Laser-Kapsulotomieraten“ April 2009

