4.3 Patients identification

Upon completion of the data collection, each patient / patient eye will be provided with a unique patient identification code. This code is used for study purposes only. During and also after completion of the study, the patient can only be identified by the study doctor or the head of study center.

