4.4 Documentation

The data is collected via the Excel program (Version 14.0.7166.5000/32-Bit, Microsoft, USA). The intraoperative information is taken from the surgical books and the respective surgical reports. The following data is recorded.

- Operation Date
- Name and address of the patient
- Date of birth
- Which eye (right/left)
- Anesthesia
- Power of the MICS-IOL
- Surgeon
- Intraoperative parameters (Phaco time, Phaco machine, Hardness of the lens, etc.)
- Intraoperative special features/complications

The postoperative documentation is taken from the charts or the questionnaire filled in by the patient. Here, the patient should indicate (if possible with a date) whether a Nd:YAG laser treatment has already been performed on the operated eye. If a patient does not provide clear information due to ignorance, then the respective registered ophthalmologist will be contacted.

In patients without a previously diagnosed or treated PCO (in the hospital or at the ophthalmologist), the information date is documented instead of the laser date. If necessary, the patient will be brought to the hospital once in order to assess the present capsule opacity.

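### The target of 388 is calculated in patients but applied in eyes as the condition for examining uncertain patients, and no rule covers two eyes of one patient (minor).

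*Combined protocol and SAP*

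**What the plan says.** Section 4.2 defines the result of its formula as "n=Subjects number", labels the resulting 388 as patients, and divides by a 13.9% response rate to get 2,792 patients. Because of the patients' age it adds that "an even lower response rate is to be expected", and continues: "For this reason, up to 3000 patients will be contacted".

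Section 4.5 uses the same figure in another unit. Patients who could not give information are brought in for examination only if "the planned number of 388 eyes is not reached by sending a questionnaire to the patients". Section 2.2 also counts in eyes: "Up to 3000 patient's eyes should be recruited".

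The eligibility criteria (2.1.1 and 2.1.2) do not restrict a patient to one eye. Section 4.3 leaves the unit open: "each patient / patient eye will be provided with a unique patient identification code". Section 4.4 records whether the right or left eye was operated. Section 5 names a Kaplan-Meier analysis of the PCO rate and gives no unit of analysis, no interval and no treatment of fellow eyes.

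**The concern.** The only derivation of 388 in the document counts patients. The only place where 388 decides anything counts eyes. The two agree if every patient contributes one eye, but the plan does not require that. Once some patients contribute two, the eye count runs ahead of the patient count. It can reach 388, and so switch off the section 4.5 examinations, while the number of patients is still short of the calculated target.

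A second consequence concerns precision. Two eyes of one patient share age, general health and often surgeon and technique, so their outcomes are probably correlated. A standard error that treats all eyes as independent is then too small. The plan neither selects one eye nor allows for the pairing.

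**Working it through.** **The plan's own figure.** Inputs from section 4.2: SD 0.492, relevant difference 0.1, response rate 13.9%.
- 16 × 0.492² / 0.1² = 387.30, rounded up to 388. The printed 387.88 corresponds to an unrounded SD of about 0.4924. Either way the result is 388.
- 388 / 0.139 = 2,791.4, rounded up to 2,792.

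Both figures reproduce. The number is not in dispute here, only its unit.

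**Patients behind 388 eyes.** Let f be the share of patients who contribute two eyes. The documents do not give f, so the values are assumptions. Patients needed = 388 / (1 + f), rounded up.
- f = 30%: 388 / 1.3 = 298.5, so 299
- f = 50%: 388 / 1.5 = 258.7, so 259
- f = 70%: 388 / 1.7 = 228.2, so 229
- f = 100%: 388 / 2 = 194

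At the other end, a single bilateral patient gives 388 eyes from 387 patients.

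**When the two counts decide differently, if the 3000 are patients (section 4.2) and every responder is evaluable.** The patient count falls short of 388 below 388 / 3000 = 12.9%. The eye count still reaches 388 down to:
- f = 30%: 299 / 3000 = 10.0%
- f = 50%: 259 / 3000 = 8.6%
- f = 70%: 229 / 3000 = 7.6%

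At 13.9%, 3000 × 0.139 = 417 patients respond and both counts pass 388. The margin to 12.9% is one percentage point. If only 90% of responders were evaluable (an assumption), the patient threshold would be 388 / 2700 = 14.4%, above the plan's rate.

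**The same, if the 3000 are eyes (section 2.2).** With f = 50%, 3000 / 1.5 = 2000 patients. At 13.9% that is 278 responders with 278 × 1.5 = 417 eyes. The eye count passes 388 and the patient count does not, at the plan's own response rate.

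**Precision.** Everything in this step rests on assumptions. If 0.492 is read as a binomial SD, p(1 − p) = 0.492² gives p = 41% or 59%; 41% was taken as the 3-year PCO rate. The simulation used:
- 388 eyes, exponential times, and 6000 runs for each of two seeds;
- follow-up of 3 to 5 years for 80% of patients (section 4.2 says 80% were operated 3 to 5 years ago) and 0.5 to 3 years for the rest;
- fellow eye operated 0 to 1 year after the first;
- Gaussian copula with latent correlation ρ between fellow eyes.

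| f | ρ | Outcome correlation at 3 years | True 95% half-width (points) | Eye-level Greenwood half-width (points) | Coverage |
|---|---|---|---|---|---|
| 0 | – | – | 5.1–5.2 | 5.1 | 94–95% |
| 30% | 0.3 | 0.19 | 5.3–5.5 | 5.2 | 94% |
| 50% | 0.5 | 0.33 | 5.7 | 5.2 | 92% |
| 70% | 0.7 | 0.49 | 6.1 | 5.2 | 90–91% |

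The mean estimate was 59.0–59.1% PCO-free against a true 59%, so the point estimate does not move.

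As a cross-check, the variance inflation is 1 + (outcome correlation) × 2f / (1 + f).
- f = 30%: 1 + 0.19 × 0.46 = 1.09
- f = 50%: 1 + 0.33 × 0.67 = 1.22
- f = 70%: 1 + 0.49 × 0.82 = 1.40

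Multiplying 5.2 by the square roots (1.04, 1.10, 1.18) gives about 5.4, 5.7 and 6.1 points, in line with the simulation.

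**The case against.** The strongest reply is that little depends on this. The main question is the PCO rate of one lens, and its point estimate does not change. No interval, test or comparison is announced, so the coverage figures concern an interval that the plan does not promise. The examinations concern only patients who are unsure of their outcome, and for them section 4.4 already provides that "then the respective registered ophthalmologist will be contacted". Only those whose ophthalmologist cannot help either would be affected, and the size of that group is not given. At 13.9% of 3000 patients, both counts lead to the same decision. All of this stands and limits the weight of the point. It does not remove the mismatch, because the plan expects a response below 13.9% and, on the section 2.2 reading, the counts can already part at 13.9%.

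It is also fair to say that section 4.4 records the eye, so outcome by eye is largely provided for. What is missing is a rule for entry and analysis, and a clear link between the two eyes of a patient.

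A reader might infer a further contradiction. Sections 2.4 and 4.4 foresee an examination where necessary without mentioning 388, and section 2.4 describes the occasion as "if no PCO was documented or if not known". The documents do not compel that reading: section 4.5 is the dedicated section and can be taken to specify when the general provision applies.

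A reader might also infer that 388 eyes must be raised to a particular larger number. The documents give neither the bilateral share nor the correlation, so they support no such number.

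**Conclusion.** The point holds as a minor inconsistency. The same 388 is a patient count where it is derived and an eye count where it is used, and bilateral patients are not covered by any rule. As written, the examinations can be switched off with as few as 194 patients. How likely that is depends on the bilateral share and the response rate. If the 3000 are patients and all responders are evaluable, the counts disagree from just under 12.9% down to about 10.0%, 8.6% or 7.6% for 30%, 50% or 70% bilateral.

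The loss of precision is modest and matters only if standard errors or an interval are reported: a true half-width of about 5.3 to 6.1 points against a nominal 5.2, with coverage falling from about 94% to 90–91%. This rests on the assumed bilateral share, correlation and 41% rate. Both effects vanish with one eye per patient.

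It would go too far to conclude that the PCO rate will be biased or that 388 is miscalculated. The estimate is essentially unaffected, and the figure reproduces from the plan's formula.

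**What to change.** 1. Use one unit for 388 in sections 4.2 and 4.5: patients, or equivalently one pre-specified eye per patient, for example the first operated.
2. In section 2.2, state the 3000 as patients contacted, in line with section 4.2.
3. State in the eligibility criteria or section 5 whether both eyes of a patient may enter. If they may, identify each eye in section 4.3 by patient ID plus an eye suffix, and give the Kaplan-Meier estimate a patient-clustered variance (robust, or a bootstrap that resamples patients).

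The operating-room books used for screening in section 4.1 would allow the bilateral share to be counted before anyone is contacted, so it need not be assumed.

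The cost is a few sentences, a little more analysis work and a slightly wider interval if one is reported. Counting patients may also trigger the examinations already foreseen in section 4.5, with the insurance cost named there, somewhat more often.

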5. STATISTICAL ANALYSIS

For data protection reasons, all data of the patient are immediately pseudonymized after collection. The head of the study center ensures that it is no longer possible to draw any conclusions about the respective patient from the data collected.

The data are evaluated with the computer program STATISTICA (Version 10, StatSoft GmbH, Hamburg, Germany) using the Kaplan-Meyer analysis.

The main question is the determination of the PCO rate after implantation of the MICS intraocular lens L-313 under the conditions prevailing in Neubrandenburg.

6. ETHICAL ASPECTS

Prior to the start of the study, a documented approval from the Greifswald Ethics Committee and the relevant regulatory authority will be obtained in accordance with local laws, regulations and authorities. If necessary, an extension, renewal or supplement to the permit must be obtained and forwarded to the sponsor.

7. SAFETY

For any adverse events that have occurred or may have occurred, the local laws and regulations as well as the reporting system of the manufacturer must be considered and followed.

7.1 Adverse events

An adverse event (AE) is an adverse medical event, accidental illness or injury, or adverse clinical sign in a study subject during the observation period, with or without association with the MICS L-313 intraocular lens.

All study eye AEs must be recorded in the data collection table. Each AE must be classified according to the degree of damage to the patient, as well as with respect to the IOL or its implantation procedure.

AEs are classified as follows:

- MILD: Complaints without interruption of the daily routine
- MODERATE: Complaints that reduce or affect daily routines
- SEVERE: Disability with inability to work or to cope with normal daily routine

Changes in a chronic condition or illness are not considered to be AEs.

Cataract surgery-related AEs to be expected are listed here:

- Anterior capsular tear
- Posterior capsular rupture
- Vitreous humor in the anterior chamber
- Intraoperativ hyphema
- Loss of vitreous humor
- Choroid bleeding, effusion or detachment
- Iris injury or trauma
- Corneal damage
- Zonular dialysis
- Fibrin reaction
- Persistent Hyphema
- Corneal clouding, corneal edema
- Retinal complications
- eye movement disorders

7.2 Severe adverse events

An AE is classified as severe without considering the relationship with the IOL when:

- If it leads to death
- If it leads to a significant deterioration of health
 - life-threatening illness
 - permanent impairment of a body part / body function
 - inpatient treatment or extension of inpatient stay is necessary
 - surgical intervention necessary

All serious adverse events (SAEs) must be reported to the sponsor within one week of the occurrence of the event.

